12. Any condition that, in the investigator's opinion, may compromise study participation, present a safety risk to the subject, or may confound the interpretation of the study results
13. A QT duration corrected for heart rate by Fridericia's formula (QTcF) > 450 millisecond (msec) for males or > 470 msec for females, based on either single or averaged QTcF values of triplicate ECGs obtained over a 3-minute interval
14. Currently enrolled in another investigational device or drug study
15. Greater than 10 days of continuous (>12 hours/day) administration of oxygen via non-invasive positive pressure ventilation or high-flow nasal cannula oxygen for hypoxic respiratory failure due to COVID-19

Investigational Products, Dosage, and Mode of Administration:

cePolyTregs will be prepared and administered under sterile conditions according to the Cell Therapy Manual.

cePolyTregs are polyclonal Treg cells that have been collected from qualified donors by leukapheresis under GMP conditions, purified to yield a population of CD4⁺CD127^{lo/-}CD25⁺ regulatory T cells, expanded using anti-CD3/anti-CD28-coated magnetic microbeads and IL-2 for 12 to 13 days, debeaded and cryopreserved in Cryostor[®] CS5 solution at a concentration of 1 x 10⁷ cells/mL. cePolyTregs are distributed to clinical study sites and stored in liquid nitrogen until use.

One or more bags are thawed immediately prior to administration, and cePolyTregs are infused by the IV route in unrelated subjects (allogeneic) according to the study protocol.

Reference Therapy, Dose and Mode of Administration:

All subjects in both parts of the study will receive standard of care treatment for COVID-19, including dexamethasone and other approved therapies for ARDS associated with SARS-CoV-2 infection per institutional guidelines.

Subjects randomized to placebo in Part 2 of this study will receive an infusion of normal saline solution at a matched volume to the cePolyTregs infusion.

Statistical Methods:

Details for the conduct of all safety, efficacy, and PD/biomarker analyses will be provided in a Statistical Analysis Plan (SAP) prior to database lock.

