8.6.3 Secondary Efficacy Endpoints

Part 2 (Phase 2a):

Efficacy of cePolyTregs compared with placebo/SOC, as assessed by:

- The proportion of subjects with a 2-point or greater improvement in the WHO severity scale for COVID-19 pulmonary syndrome on each of Study Days 7, 14, 21, and 28
- The proportion of subjects with improvement in the WHO severity scale for COVID-19 pulmonary syndrome to Grade 3 or less on each of Study Days 7, 14, 21, and 28
- The proportion of subjects requiring mechanical ventilation on each of Study Days 7, 14, 21 and 28
- Number of days free of mechanical ventilation on Days 29 and 57
- Mean and median Sequential Organ Failure [SOFA] scores on each of Study Days 7, 14, 21 and 28
- Change in chest imaging (radiograph or CT scan) abnormalities
- All-cause mortality on Study Days 29 and 84

Parts 1 and 2:

Pharmacodynamic and biomarker changes associated with administration of cePolyTregs compared with placebo/SOC, including but not limited to:

- Change from baseline in circulating cePolyTregs
- Change from baseline in pulmonary cePolyTregs by endotracheal aspirate and mini BAL

UCSF	Clinical Study Protocol No. UCSF-cePolyTregs-01	Page 35 of 72
------	---	---------------

- Change from baseline in ferritin, C-reactive protein, LDH, and high-sensitivity troponin I (hs-TnI)
- Change from baseline in d-dimer
- Change from baseline in absolute lymphocyte count
- Change from baseline in C3, C4, and CH50
- Change from baseline in inflammatory cytokines/chemokines, e.g. IL-6, IL-12, IFN γ , TNF α , MCP-1 and MCP-4
- Phenotypic and functional changes from baseline in immune subsets using cytometric, genomic and/or proteomic analyses of cells harvested from endotracheal tubes, mini BAL, and blood

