9 STUDY POPULATION

Each cohort will enroll unique subjects who may not be treated in more than 1 cohort.

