11.11 Exploratory Pharmacokinetic and Pharmacodynamic Biomarkers

Table 4 summarizes laboratory mechanistic analyses for assessing PK and PD of cePolyTregs using samples collected as described in the SOE.

Table 4. Mechanistic Assessments of cePolyTregs PK and PD

PK Markers
Change from baseline in circulating cePolyTregs
Change from baseline in pulmonary cePolyTregs by endotracheal aspirate and mini BAL
cePolyTregs expansion and activation using scRNA/TCR-sequencing
PD Markers
Change from baseline in acute phase reactants, e.g. ferritin, C-reactive protein, LDH, and albumin
Change from baseline in endothelial cell injury markers, e.g. d-dimer, soluble thrombomodulin, VWF, and angiopoietin-2
Change from baseline in lung epithelial cell and other tissue injury markers, e.g. RAGE, KL-6, SF-D, and troponin I
Change from baseline in absolute lymphocyte count
Change from baseline in inflammatory markers, e.g. IL-6, IL-12, IFN γ , GM-CSF, TNF α , IP10, MCP-1, MCP3, C3, C4, CH50, and MCP-4
Phenotypic and functional changes from baseline in immune subsets using cytometric, genomic and/or proteomic analyses of cells harvested from endotracheal tubes, mini BAL and blood
Anti-SARS-CoV-2 T cell immunity
Anti-SARS-CoV-2 humoral immunity

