APPENDIX C Mechanistic Assessments

Assay	Specific Readout	Comparisons
Assays based on flow cytometry and qPCR to detect cePolyTregs in blood of treated subjects	Percent of endogenous CD4 T cells and Treg	% change from baseline among treatment groups and temporal PK information
Assays based on flow cytometry and qPCR to detect cePolyTregs in the Pulmonary tissue (endotracheal aspirate and mini BAL)	Percent of endogenous CD4 T cells and Treg	% change from baseline among treatment groups and temporal PK information
Flow cytometric, genomic and/or proteomic analyses of cells harvested from endotracheal tubes and mini BAL and blood to determine phenotypic changes in immune subsets	Percent of individual immune subset, expression of activation and memory markers	% change from baseline among treatment groups
Flow cytometric, cell culture and expression analyses of cells harvested from endotracheal tubes and mini BAL and blood to determine functional changes in immune subsets	Functional activities of individual immune subset including cytokine production, cytotoxicity and other immune activities	% change from baseline among treatment groups
C-reactive protein and LDH per clinical laboratory standard methods	Concentrations	% change from baseline among treatment groups and temporal biomarker information
d-dimer per clinical laboratory standard methods	Concentrations	% change from baseline among treatment groups and temporal biomarker information
Albumin per clinical laboratory standard methods	Concentrations	% change from baseline among treatment groups
Troponin I per clinical laboratory standard methods	Concentrations	% change from baseline among treatment groups
Assays for inflammatory cytokines/chemokines, e.g. IL-6, IL-12, IFN γ , GM-CSF, TNF α , IP10, MCP-1, MCP3, and MCP-4	Concentrations	% change from baseline among treatment groups
Frequencies and neutralization activities of SARS-CoV-2-specific antibodies	Titer	% change from baseline among treatment groups
Frequencies and effector function of SARS-CoV-2-specific T cell responses	Percentages of CD4 and CD8 T cells that respond to SARS-CoV-2 antigens, effector molecule expression	% change from baseline among treatment groups

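### Appendix C compares infused-cell levels by percent change from a baseline that is zero by design, and this does not match the plain change from baseline in Section 8.6.3 and Table 4

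*Combined protocol and SAP*

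**What the plan says.** Appendix C has two rows on detecting the infused product: "Assays based on flow cytometry and qPCR to detect cePolyTregs in blood of treated subjects", and a matching row for endotracheal aspirate and mini BAL. In both, the readout is "Percent of endogenous CD4 T cells and Treg" and the comparison is a percent sign followed by "change from baseline among treatment groups and temporal PK information".

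The endpoint list in Section 8.6.3 has "Change from baseline in circulating cePolyTregs" and a corresponding lung item. Table 4 in Section 11.11 has "Change from baseline in pulmonary cePolyTregs by endotracheal aspirate and mini BAL" among its PK markers. Neither place uses a percent sign.

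Section 13.1 refers the assessment of PD and biomarker data to Appendix C, and Section 13.7 does the same for the detailed PD analyses. Section 13 has no PK analysis subsection. Section 13.3.1 exempts PK summaries from the safety population, but no PK population is defined. Within the protocol, Appendix C is therefore the only place that says how these readouts will be compared between groups. The synopsis and Section 13 leave further detail to a separate SAP.

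**The concern.** Percent change needs a non-zero baseline. Here the analyte is the investigational product itself, sampled before the only infusion, so there should be none of it to measure. A statistic that divides by that baseline has no value at the true level. Where assay noise yields a small positive reading, the result depends mainly on the noise.

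At stake is the between-group (or, in Part 1, between-dose) summary of exposure in blood and lung. These are listed secondary endpoints, and Table 4 markers are among the data that may be considered when the recommended Phase 2 dose is chosen. If the SAP inherited the Appendix C wording, the programmer would have to improvise: drop subjects, add an arbitrary constant, or switch measure after seeing the data.

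**Working it through.** The plan gives no figure to reproduce on this point. The check is whether the stated measure is defined for these two readouts.

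**Step 1: the baseline level.**
- Source of cells: "cePolyTregs are infused by the IV route in unrelated subjects (allogeneic) according to the study protocol" (synopsis).
- Baseline sampling: the Schedule of Events marks whole blood, endotracheal aspirate and mini BAL in the Day 0 pre-dose column.
- Earlier exposure within the study: "Each cohort will enroll unique subjects who may not be treated in more than 1 cohort" (Section 9).
- Earlier exposure elsewhere: Section 8.2 says that the product has not been used in any clinical study.
- Other donor grafts: exclusion criterion 8 (Section 9.2) removes prior bone marrow or stem cell transplantation.

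Together these leave no source of cePolyTregs before infusion, so the true baseline is 0. No section says this in words.

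**Step 2: the stated measure at that baseline.** Percent change = 100 × (post − baseline) / baseline. With baseline = 0:
- a subject with detectable cells at level x > 0 gives 100 × x / 0, undefined;
- a placebo subject, or a treated subject with none detected, gives 0 / 0, undefined.

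**Step 3: if the assay reads slightly above zero before infusion.** The protocol gives no detection limit, so the backgrounds and post-infusion levels below are assumptions, expressed as a percentage of endogenous cells.

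| Post level | Baseline reading | Percent change | Absolute change (points) |
|---|---|---|---|
| 1% | 0.001% | 100 × 0.999 / 0.001 = +99,900% | 0.999 |
| 1% | 0.01% | 100 × 0.99 / 0.01 = +9,900% | 0.99 |
| 1% | 0.1% | 100 × 0.90 / 0.1 = +900% | 0.90 |
| 5% | 0.1% | 100 × 4.9 / 0.1 = +4,900% | 4.9 |

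In the first three rows the post-infusion level is the same, yet the percent change varies 111-fold (99,900 / 900 = 111) with background alone. The absolute change moves by about a tenth. The first and last rows show that the ranking can also reverse: a subject at 5% scores lower than one at 1%.

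**Step 4: the measure named elsewhere.** Plain change = post − baseline. With baseline 0 and assumed post levels of 0%, 0.1%, 1% and 5%, it gives 0, 0.1, 1 and 5 percentage points. It is always defined and equals the observed level.

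**Step 5: how many subjects.** The blood row is limited to treated subjects. If that means cePolyTregs recipients, the planned ceiling is 18 in Part 1 plus 50 in Part 2, or 68. For lung samples the number is smaller and falls over time, because Schedule of Events footnotes k and l end collection at removal of the endotracheal tube and leave mini BAL to the investigator's discretion.

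**The case against.** Four counter-arguments deserve an answer.

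**The same cells also promise temporal PK information.** They do, and the readout column names the measured fraction, so following it over time is within the plan. A reader might infer from Step 2 that infused-cell exposure cannot be analysed at all. The documents do not support that: only the percent-change comparison fails, and the endpoint as worded in Section 8.6.3 and Table 4 is computable. What stands is that the temporal part names no summary (peak, area, last detectable day), and that Appendix C disagrees with the endpoint list.

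**The percent sign may mean percentage points, since the readout is already a percentage.** This is possible. However, Appendix C applies the same phrase to concentrations and a titre, where it can only mean relative change. If points were intended in two rows, those rows must say so.

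**The phrase is generic column wording.** It appears in all 11 rows, including composite readouts with no single number, so it may not be a deliberate choice of estimator. That makes the slip easier to explain, but it is still the text that Section 13 points to.

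**The SAP will settle it.** It may. That makes it sensible to correct the wording before the SAP takes it over.

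A reader might also infer that the dose recommendation is compromised. The synopsis defines the recommended Phase 2 dose by PD effect, using markers that may include those in Table 4, and Table 4 lists cePolyTregs levels under PK, apart from PD. Section 8.7 cites Table 4 data only as part of a wider judgement. Nothing makes the dose depend on a percent change in cePolyTregs.

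**Conclusion.** The point holds for two cells of Appendix C. In the blood and lung cePolyTregs rows, percent change from baseline is undefined at the true pre-infusion level and would be dominated by assay background if a small reading occurred. It also conflicts with the plain change from baseline given for the same markers in Section 8.6.3 and Table 4.

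The conclusion rests on a zero baseline inferred from the design. It is exact for the true level. A reader might take it to mean that no subject could ever yield a value, but the documents do not establish what each assay will read before infusion. The numbers affected are at most the subjects sampled, not all those enrolled.

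The zero-by-design argument does not extend to the other Appendix C rows, which measure the subject's own markers. Percent change there is not an error.

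This is a minor matter of specification. The primary endpoint, the 10% two-sided error rate and the sample size of 100 are unaffected.

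**What to change.** In the two cePolyTregs rows of Appendix C:
- replace percent change from baseline with the observed donor-cell fraction at each scheduled time point (equivalently, at zero baseline, the absolute change in percentage points);
- name the summaries: peak, area under the curve, and last day detectable;
- state how values below detection are handled, including a positive pre-dose reading;
- align the wording with Section 8.6.3 and Table 4, and carry it into the SAP.

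This changes text only. It needs no new samples, visits or subjects.

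A separate, optional improvement concerns the concentration markers (for example C-reactive protein, d-dimer and the cytokines): analyse the log ratio to baseline with log baseline as a covariate. It uses data already collected. The small cost is that results are reported as geometric mean ratios and that values below detection need a rule there too.
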